The instrument can also be completed by parents but their assessments tend to be give higher ratings for the child’s abilities. We are not in a position to evaluate the extent to which assessments by childcare staff might correspond with assessments by teachers. Despite this limitation, the assessments are being carried out by the same childcare staff at baseline and follow-up and this provides a consistent basis for comparing change in the intervening period.

In addition to the EDI, the Child Questionnaire includes a measure of the child's emotional regulation using the Emotion Regulation Checklist (ERC)⁸⁰. This is based on a growing body of evidence which suggests that a child's capacity for emotional self-regulation is a strong predictor of well-being generally⁸¹ as well as school-readiness and school outcomes⁸², and has been used in the assessment of pre-school children⁸³.

The Child Questionnaire also contains a measure of inter-agency working based on the rationale that, where this occurs, it will manifest at the front-line of service delivery for children and their parents. Three questions are used to measure inter-agency working: (i) has there been any contact with any other agency or service about the needs of this child during the previous four weeks; (ii) how many times there has been contact during the previous four weeks; and (iii) whether the response has been helpful. The questions, as worded, are suitable for the baseline (since some children may only be known to the childcare centre for 4 weeks) but will be adjusted to give a longer timeframe in the follow-up (since all children will be in the childcare centre for the previous school year). A similar set of questions are also asked in the Staff Questionnaire (Section D). Aspects of inter-agency working are also covered in the Parent Questionnaire (H2.6: 'Staff help me to contact other services when I need to') with a matched item in Staff Questionnaire (D3.6: 'I help parents to contact other services when they need to').

80 Shields and Cicchetti, 1997.

81 The results of a recently published longitudinal study - based on the Dunedin Multidisciplinary Health and Development Study which tracked 1,037 children from birth (in 1972/3) to 32 years with 96% retention rate - found that 'childhood self-control predicts physical health, substance dependence, personal finances, and criminal offending outcomes, following a gradient of self-control. Effects of children's self-control could be disentangled from their intelligence and social class as well as from mistakes they made as adolescents' (Moffitt, et al, 2011:2693). The same study included analysis of a cohort of 500 sibling-pairs - based on the Environmental Risk Longitudinal Twin Study (E-Risk) in England and Wales which tracks the development of a representative birth cohort of 2,232 twin children born in 1994/5 - found that 'the sibling with lower self-control had poorer outcomes, despite shared family background. Interventions addressing self-control might reduce a panoply of societal costs, save taxpayers money, and promote prosperity' (Ibid).

82 This is a major finding of The Effective Provision of Pre-School Education (EPPE) research project which is a 12-year, mixed-method research design following the progress of over 3000 children, aged 3-11 years in 141 pre-schools and 800 primary schools across England since its inception in 1996. 'The EPPE has found that that the strongest predictor of children's resilience to disadvantage is in their level of 'Self-regulation' (or 'Independence and Concentration') at the start of school (Sylva et al., 2008). Additionally, the early years HLE [Home Learning Environment] also has a strong and long-lasting effect on children's later self-regulation (Sammons et al., 2007). Self-regulation in this study was measured by questions about the child's willingness to 'work things out for themselves', 'seeing task through to the end' and 'persevering in face of difficulty.' (Siraj-Blatchford, 2010b:471-2). Building on the concept of self-regulation, the EPPE study distinguished between 'mastery-oriented' and 'helpless-oriented' children noting that: "Helpless' children have been found to be less persistent; they give up easily as they worry about their lack of ability. But when 'mastery oriented' children experience a setback; they tend to focus on effort and strategies instead of worrying that they are incompetent. These dispositions to learn seem to be very powerful and are associated with the development of positive early personal and social identities. Positive dispositions have been found to provide resilience (Werner & Smith, 1982; Claxton, 1999) and to lead to positive lifelong 'learning trajectories' (Gorard et al., 1999).' (Ibid). See also Shields, Dickstein, Seifer, Giusti, Dodge-Magee and Spritz, 2001; Fantuzo, Bulotsky-Shearer, Fusco and McWayne, 2005.

83 Fantuzo, Bulotsky-Shearer, Fusco and McWayne, 2005.

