11 The focus of the evaluation on interventions which are 'substantial and sustained' is informed by Bronfenbrenner's proposition that: 'Especially in its early phases, but also throughout the life course, human development takes place through ... interaction To be effective, the interaction must occur on a fairly regular basis over extended periods of time' (Bronfenbrenner and Morris, 2006:797). This proposition is also consistent with the scientific understanding of how the brain functions: 'All functional capacities in the brain are dependent to some degree upon the presence of appropriately timed, appropriately patterned signals that will specifically stimulate the neural systems mediating that function. Patterned, repetitive activity changes the brain. A child exposed to consistent, predictable, nurturing, and enriched experiences will develop neurobiological capabilities that will increase the child's chance for health, happiness, productivity and creativity. If a child is neglected – if he or she hears fewer words, has fewer relational opportunities, receives less physical comfort, and has less love – the rapidly organizing networks in the brain that mediate language, social affiliation, and attachment will not receive sufficient patterned, repetitive activation to develop normally. The therapeutic implications of this ... cannot be overstated. Repetition, repetition, repetition: Neural systems – and children – change with repetition' (Perry, 2006:36-37).

Table 1 List of Projects in the National Early Years Access Initiative

ID	Location	Name	Lead Agency	Intervention for Evaluation
BC	Ballyfermot / Chapelizod	Early Years Language & Learning Initiative	Partnership	Train and mentor childcare staff in Hanen Programme to: (i) Improve the child's language development (ii) Support parents to encourage the child's language development
CC	Canal Communities	Bringing It All Back Home	Daughters of Charity	Train and mentor childcare staff in Marte Meo Programme and Incredible Years Programme to: (i) Improve the child and parent outcomes (ii) do intensive outreach with children and their parents
CK	Cork	Happy Talk Project	Partnership	Train childcare staff in Hanen Programme to: (i) Improve the child's language development (ii) Support parents to encourage the child's language development
CN	Clondalkin	Addressing Gaps in Training & Practice	Partnership	Mentor childcare staff to improve outcomes for children and their parents

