13 For that reason, the proper use of a logic model requires awareness of its limitations since 'the logic model is a model – not reality. It depicts assumed causal connections not true cause-effect relationships' (Taylor-Powell & Henert, 2008). Limitations of logic modelling include the following: (i) a logic model represents intention, it is not reality; (ii) it focuses on expected outcomes so people may overlook unintended outcomes (positive and negative); (iii) it focuses on positive change – change isn't always positive; (iv) it may simplify the complex nature of causal attribution where many factors influence process and outcomes; (v) it doesn't address whether we are doing the right thing – we may get caught up in creating a logic model and lose track of whether the program is the right thing to do; and (vi) may stifle creativity and spontaneity. (Ibid).

The left-hand side of the logic model depicts the inputs of NEYAI and are constituted by the 11 project interventions. These include both the actual services delivered to children and their parents as well as the training and mentoring of staff to deliver those services. These inputs will vary by type, duration and intensity but will also vary in the manner of their implementation. The context of each project, particularly the focus on children living in disadvantaged areas, can also be regarded as an 'input' in the sense that the uptake and effectiveness of each intervention is likely to be affected by characteristics of the target group and the target area. In this sense, context provides important information about how NEYAI is targeted, who participates, and how it influences outcomes directly and indirectly for parents and children (see Section 6.5 below).

The right-hand side of the logic model depicts the outcomes which are conceptualised as improved well-being for children and their parents. For children, this takes the form of improved physical, emotional, social and cognitive development. For parents, it includes improved individual well-being, both physical and mental, as well as improved parenting and family relationships but may also include an improved sense of social support.

Figure 1 Logic Model of National Early Years Access Initiative

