6.1 Child Questionnaire

The purpose of the Child Questionnaire is to assess the well-being of each child across a wide range of domains that are recognised as central to child development including: physical health; social competence; emotional maturity and regulation; language and cognitive skills; communication skills. The assessment of the child will be carried out in the childcare centre, jointly by the Childcare Leader and Childcare Worker who have a thorough knowledge of the child, and must know the child for at least a month. The questionnaire requires that answers are based on careful and reliable observation of all aspects of the child's development. Results of the Child Questionnaire are entered on-line by childcare staff. The Child Questionnaire was piloted in two childcare settings – none of which are part of this evaluation - and it can be completed in about half an hour.

The conceptual framework underpinning the Child Questionnaire is graphically illustrated in Figure 3. There is a detailed guide to every question in Appendix Three and the actual questionnaire is in a separate document. The left-hand-side of Figure 3 illustrates our theoretical understanding of the constituent elements of child well-being while the right-hand-side illustrates its likely determinants. This understanding, though not new or different from existing paradigms of child well-being, is a working hypothesis that will be tested against the data (see Section 9 below).

The main instrument within the Child Questionnaire is the Early Development Instrument (EDI). The EDI was developed at the Offord Centre for Child Studies at McMaster University in Hamilton, Canada. It has been validated as a measure of children's readiness to learn at school, based on data from over 16,000 Canadian children, collected in the spring of 1999⁷⁵. The EDI has been tested in both pre-school and school settings and there is a 'high inter-rater reliability' between the scores of early childhood educators and teachers⁷⁶. In Ireland, the EDI is being used to evaluate the Preparing for Life Programme by UCD Geary Institute⁷⁷ and has been used in a city-wide study of

75 Janus, Brinkman, Duku, Hertzman, Santos, Sayers, and Schroeder, 2007; Janus and Offord, 2007.

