Communication and language	0.03	-0.08 to 0.14	0.61	0.03
Problem-solving, reasoning, numeracy	0.04	-0.07 to 0.15	0.49	0.04
Knowledge/ understanding of the world	-0.02	-0.13 to 0.09	0.70	0.02
Physical development	-0.05	-0.16 to 0.05	0.33	0.05
Creative development	0.00	-0.12 to 0.11	0.99	0.00
Foundation profile score total	0.01	-0.09 to 0.11	0.83	0.01
Maternal Wellbeing				
Mother's satisfaction with life	0.21	0.08 to 0.33	0.00	0.10
Mother's rating of safety in area	0.03	-0.03 to 0.10	0.27	0.03
Mother's self rated depression	0.40	0.14 to 0.65	0.00	0.09
Parent and Family Functioning				
Harsh discipline in home	-0.13	-0.18 to -0.08	0.00	0.24
Chaos in home	-0.24	-0.36 to -0.13	0.00	0.29
Home learning environment	0.17	0.09 to 0.24	0.00	0.27
	Odds ratio	95% CI	p	
Parents attended school meetings	- 0.43	-0.34 to- 0.56	0.00	

(i) Effects are adjusted for child, family and area characteristics and strata.

(ii) The mean effect size across all three sets of analyses for those outcomes which were significantly related to SSLP status across all three sets of analyses.

CI=Confidence interval

Results in bold italics are replicated as statistically significant across all 3 data sets.

Source: National Evaluation of Sure Start Team, 2010:29.

Guidelines for Project Coordinators to Support the Evaluation

1. Coordinators are the link between the childcare centres and the Evaluation Team. As such, they have a key role to play in ensuring that the evaluation is carried out as planned and agreed. The core of the evaluation is based on data collected using three questionnaires: Staff Questionnaire, Child Questionnaire, and Parent Questionnaire. These questionnaires are completed at baseline (at a time to be agreed with each project but always **before** any intervention begins but not later than October 2012) and at follow-up (again, at a time to be agreed with each project but not later than June 2013). Coordinators have a particularly central role in data-collection using the Staff Questionnaire and the Child Questionnaire as well as keeping an accurate record of the intervention which is being implemented in their project. The Parent Questionnaire will be administered by an independent team of interviewers.

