E3.1-3.25	Behaviour and Emotional Difficulties	Strengths and Difficulties Questionnaire (SDQ) ¹⁴¹ (version for 3-4 year olds to be completed by parent) comprising 25 items on its core scale which has five sub-scales: (i) conduct problems (ii) emotional symptoms (iii) hyperactivity (iv) peer problems (v) prosocial behaviour. Note that items 18 ('often argumentative with adults'), 21 ('can stop and think things over before acting') and 22 ('can be spiteful to others') are slightly different to the 4-16 year old version of SDQ.	✓	✓
E4.1-4.20	Temperament	Emotionality, Activity and Sociability Questionnaire (EAS) ¹⁴² (version to be completed by parent) comprising 20 items on its core scale which has three sub-scales: (i) emotionality (ii) activity (iii) sociability.	✓	
E5.1	Concerns about how the child talks	GUI scale ¹⁴³	✓	
E5.2	Child has a specific learning difficulty	GUI scale ¹⁴⁴	✓	
E6.1-6.21	Child's diet	GUI scale	✓	

140 A recent analysis defined the prevalence of Special Education Needs (SEN) by reference to E2.2, E2.3, E5.1, E5.2 (See Banks and McCoy, 2011:85-104).

141 For more information, see www.sdqinfo.com; see also Goodman, 1997; Goodman, Meltzer and Bailey, 1998; Goodman and Scott, 1999; Goodman, 1999; Smedje, Broman, Hetta and von Knorring, 1999.

142 Buss and Plomin, 1984.

143 A recent analysis defined the prevalence of Special Education Needs (SEN) by reference to E2.2, E2.3, E5.1, E5.2 (See Banks and McCoy, 2011:85-104).

144 A recent analysis defined the prevalence of Special Education Needs (SEN) by reference to E2.2, E2.3, E5.1, E5.2 (See Banks and McCoy, 2011:85-104).

SECTION F: Relationship with Your Child				
F1.1	Having fun with child	Pianta Child-Parent Relationship Scale ¹⁴⁵	✓	
F2.1-F2.30	Child-Parent Relationship	Pianta Student-Teacher Relationship Scale ¹⁴⁶ as used in Sure Start Evaluation ¹⁴⁷	✓	
F3.1-F3.2	Breastfeeding	GUI scale	✓	
F4.1-4.5	Family time together	GUI scale	✓	
F5.1-5.4	TV, etc in child's bedroom	GUI scale	✓	
F6.1-6.5	Home Learning Environment	Home Learning Environment (HLE) Scale ¹⁴⁸		
F7.1-7.4	Home Chaos	Confusion, Hubbub and Order Scale ¹⁴⁹ , used in Sure Start evaluation ¹⁵⁰		
F8.1-8.18	Parental Stress	Parental Stress Scale ¹⁵¹ comprising 18 items representing positive aspects of parenthood (emotional benefits, self-enrichment, personal development) and negative aspects (demands on resources, opportunity costs and restrictions).	✓ GUI Nine-month cohort only	

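### Having the same childcare staff rate the child twice does not by itself secure the net-impact comparison, because NEYAI trains, mentors or supports childcare staff between the two ratings

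*Protocol*

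**What the plan says.** - **Who rates.** Under Section 6.1 the child is assessed in the centre "jointly by the Childcare Leader and Childcare Worker who have a thorough knowledge of the child". They complete the Early Development Instrument (EDI), described as the main instrument of the Child Questionnaire, and the Emotion Regulation Checklist (ERC). Appendix Two, item 10, repeats the joint rating.
- **What the intervention acts on.** Section 3 counts as programme inputs the services delivered to families "as well as the training and mentoring of staff to deliver those services". In Table 1 the BC and RO entries begin "Train and mentor childcare staff in Hanen Programme to", and the CN entry reads "Mentor childcare staff to improve outcomes for children and their parents".
- **When.** Section 7 and Appendix Two place baseline before the intervention and follow-up after it.
- **What is compared.** Section 4.3 defines net impact as the difference in change between the treatment group and a group receiving usual treatment.
- **What is claimed.** Section 6.1 acknowledges that agreement between childcare staff and teachers cannot be checked. It then offers as reassurance that "the assessments are being carried out by the same childcare staff at baseline and follow-up and this provides a consistent basis for comparing change".
- **Other child measures.** Appendix Four includes the Strengths and Difficulties Questionnaire (SDQ), "version for 3-4 year olds to be completed by parent", and an item on concern about how the child talks (E5.1). Appendix Two says: "The Parent Questionnaire will be administered by an independent team of interviewers".

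**The concern.** Two ratings by the same person cancel whatever is constant in that person. They do not cancel a change in the person between the ratings. Here the programme aims to change childcare staff, and staff also provide the child score. Training could raise scores through expectation or investment in the project. It could also lower them, because staff become better at noticing language or behaviour difficulties.

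Three uses of the data are exposed:

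- The net impact of Section 4.3 on the EDI and ERC would mix change in the child with change in the rater.
- The specificity criterion of Section 4.4 treats a larger effect on cognitive outcomes in language or numeracy projects as causal evidence. Staff trained in language or numeracy might re-score those very items.
- The pathway models of Section 9.2.3 relate staff capacity to child outcomes. Staff in the same centres report their own capacity and also rate the child, so a rating shift could appear as a pathway.

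The limitation in Section 11 covers self-report and the lack of direct observation. Section 6.3 raises self-report bias only for the Staff Questionnaire. Neither says that the child's raters may themselves be changed by the programme.

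**Working it through.** **1. How far raters are exposed.** Ten of the 11 entries in Table 1 name childcare staff as the people trained, mentored or supported (BC, CC, CK, CN, DD, FL, DL, LK, LD, RO). TT refers to delivering training without naming the trainees. FL trains staff to run parenting courses, which is further from the skills used in rating a child. Table 1 does not show that each rating Leader or Worker is among those trained.

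**2. Why change scores do not remove the shift.** Write the observed mean change in an arm as true change plus rater change:

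- treatment: T₁ + r₁
- comparison: T₀ + r₀
- net impact: (T₁ − T₀) + (r₁ − r₀)

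A constant rater bias contributes nothing to r₁ or r₀. A change caused by the intervention enters r₁, and nothing in the design makes r₀ equal to it. Adjusting for measured characteristics does not help, because rater change is not a measured covariate.

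**3. The plan's own figures.** 11 × 35 = 385 per group, and 2 × 385 = 770. Section 5 gives power 0.8, p = 0.05 and effects of 0.2 to 0.5; a two-sided test is assumed here. For 0.2 SD, n = 2(1.960 + 0.842)²/0.2² ≈ 393 per group. With 385 per group, SE = √(2/385) = 0.0721, 0.20/0.0721 = 2.775, and power = Φ(2.775 − 1.960) = 0.792. So 385 roughly matches the lower end of the target before clustering and dropout.

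**4. Illustration of scale.** The shift b is assumed; the protocol gives no value. With zero true effect and b in the treatment arm only, in SD units of the analysed score, SE = √(2 × DE/385), where DE is the design effect, and

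P(p<0.05) = 1 − Φ(1.96 − b/SE) + Φ(−1.96 − b/SE).

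| Assumed shift b (SD) | DE = 1, SE 0.0721 | DE = 2 (assumed), SE 0.1019 |
|---|---|---|
| 0 | 5.0% | 5.0% |
| 0.05 | 10.7% | 7.8% |
| 0.10 | 28.4% | 16.5% |
| 0.15 | 54.8% | 31.3% |
| 0.20 | 79.2% | 50.1% |

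A shift of 0.20 SD is declared significant as often as a true effect of 0.20 SD, because the contrast cannot tell them apart. The opposite direction also matters. A true effect of 0.20 SD with a downward shift of 0.10 leaves 0.20 − 0.10 = 0.10 SD, and the unclustered chance of significance falls from 79.2% to about 28%.

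**The case against.** The sentence in Section 6.1 answers a narrower worry, whether childcare staff rate as teachers would, and for a stable difference in level it is right. Sections 6.3 and 11 already disclose reliance on self-report and give the budgetary reason for not observing directly. The plan also has child data that do not depend on staff judgement in the same way: the parent-reported SDQ, temperament and health items, and measured height and weight. All of this stands. It makes the sentence incomplete rather than simply false, and calls for restating it rather than removing it.

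Four stronger readings are tempting, and the protocol does not support them.

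- *All 11 projects, every rater, and the treatment arm only.* TT names no trainees, FL is a weaker case, and individual raters are not shown to be trained. Section 5.2 admits that usual treatment is not known, so some training may occur in comparison centres.
- *A child impact would be nothing but rater shift.* No size is given, and no single child outcome is named as primary.
- *Appendix One measures the bias.* One programme's SDQ effects there were 0.30 by parent and 0.16 by teacher. That is a spread between informants, who may see different behaviour at home and in the setting. It is not a change in one rater's standard after training.
- *A child impact should count only if the SDQ agrees in direction.* The SDQ omits language and numeracy, which BC, CK, RO and DD target, so the rule could reject the pattern Section 4.4 would regard as supportive. Parents are themselves targeted in BC, CC, CK, DD, FL, LK and RO, 7 of 11 projects. With no true SDQ effect, the sign would still agree about half the time.

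**Conclusion.** The point stands in limited form. Using the same raters removes stable rater differences, but not rater change brought about by the intervention. The reassurance in Section 6.1 therefore does not extend to the between-group difference in change on the EDI and ERC, or to the specificity and pathway arguments built on it. No other part of the protocol closes the gap.

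This rests on the protocol's own account of who rates, when, and what the projects do, plus the judgement that training can alter how staff rate. The size and direction of any shift cannot be derived from the document. The range of about 11% to 79% (8% to 50% with a design effect of 2) shows only what assumed shifts of 0.05 to 0.20 SD would do; it does not estimate what will happen.

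**What to change.** 1. **Section 6.1 and Section 11.** State that using the same raters removes stable rater differences but not rater change caused by the intervention. List this in Section 11 as a limit on conclusions from staff-rated child outcomes, and on the specificity and pathway arguments that rest on them.
2. **Sections 9.2.2 and 9.2.3.** Keep staff-rated and parent-reported child outcomes as separate outcomes; a latent variable that pooled them would hide any disagreement. Report net impact on the EDI and ERC beside the SDQ and item E5.1, as supporting evidence and not as a veto. Note there that the SDQ does not cover language or numeracy, and that parents are also targeted in the seven projects listed above.
3. **Section 9.2.1.** When the latent variables are recalibrated, test measurement invariance of the staff-rated ones by arm as well as by time. Say plainly that this can detect re-scoring of particular items but not a uniform shift across items, so passing the test does not remove the limitation in step 1.

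No new data collection or assessors are needed. The cost is a little more analysis and a more cautious statement of child impact.
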